4.10 Material required for conducting the clinical investigation

The medical device necessary for conducting the investigation is MD-Shoulder *Collagen Medical Device* (GUNA, Milan-Italy) in 2 ml vials.

This material will be sent by Guna S.p.a. to the Pharmacy of the Experimental Centre with temperature-controlled shipment (range 15°-25°C) and in a quantity suitable for conducting the Clinical Investigation.

The medical devices will have to be stored by the Experimental Centre pharmacy and subsequently by the investigators within the same temperature range.

4.11 Study group

Only one experimental group is included in the investigation plan, which will be treated with 2 ml volume ultrasound-guided infiltrations of MD-Shoulder *Collagen Medical Device* (GUNA, Milan-Italy). Composition per 2 ml: collagen 100 micrograms.

Excipients: Iris, NaCl, Water for injection. Subjects will be treated with no. 1 ultrasound infiltration at the time of enrolment, 2 weeks after enrolment and 4 weeks after enrolment.

4.12 Infiltration technique

Intra-articular infiltration will be performed with 5cc syringes and 22-gauge needles.

MD-Shoulder *Collagen Medical Device* will be infiltrated inside the scapulo-humeral joint under conditions of complete asepsis.

4.13.1 Effectiveness Criteria

4.13.2 Primary End Point

The primary End Point will consist of the evaluation, by means of the Constant-Murley Functional Scale (CMS), of the effectiveness, in terms of performance, of MD-Shoulder *Collagen Medical Device* in the recovery of joint function and reduction of associated pain at time months 3, i.e. 3 months after the first infiltration, compared to baseline (day 0). An increase of at least 15 points on the CMS scale is considered clinically significant.

4.13.3 Secondary End Points

The Secondary Endpoints will consist of evaluating the performance of MD-Shoulder *Collagen Medical Device* through:

- CMS at months 3, 6 and months 12 compared to day 0.
- NRS at week 2, week 4, months 3, months 6, months 12 compared to day 0
- ASES, SST and ROM at months 3, months 6, months 12 compared to day 0
- cuff integrity at months 12 compared to day 0 by performing MRI of the treated shoulder
- analgesic consumption at various phases of the study.
- evaluation of Adverse Events.

4.14 Data collection

All data resulting from the Clinical Investigation will be entered, within seven days of their collection, into the electronic Data Collection Form (e-CRF) "Pheedit Dedagroup" provided by the Sponsor. Radiological data will be collected and stored digitally on the PACS system. Data entry procedures will be performed by the Data Manager.

4.15 Early abandonment of the Clinical Study

I Subjects may leave the Clinical study for the following reasons:

- a. at their own request (even without justification);
- b. at the investigator's discretion.
- c. if they experience an Adverse Event.

The reason for abandonment will be stated in the e-CRF.

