5.2.2 Primary Endpoint

The primary endpoint will be assessed by Student's t-test for paired data as already established in the section on sample size.

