6.4 Adverse Events

An Adverse Event is defined as any harmful clinical event that will occur during the course of the clinical investigation in one of the subjects comprising the study population who has undergone one of the treatments in the investigation plan.

Adverse events will be classified into serious (SAE) non-serious (AE) and Suspected Serious and Unexpected Adverse Reactions (SUSAR).

An Adverse Event is defined as serious if (ICH-GCP DM 15/07/1997):

- it causes the death of the subject involved in the investigation
- places the subject's life in danger
- is such as to require hospitalization
- is such as to require prolonged hospitalization
- is such as to cause permanent or temporary disability
- leads to a congenital anomaly or birth defect

In all other cases, the Adverse Event will be non-serious and will be classified as:

- *mild* does not interfere with normal activities of daily living and resolves spontaneously.

- *moderate*, interferes with activities of daily living but resolves spontaneously;
- *severe*, prevents daily life activities and does not resolve spontaneously.

All personnel who come in contact with study subjects must report Adverse Events reported by subjects to the Investigator, who has a duty to collect all possible data about them.

- Adverse events (AEs) will be reported within 48 h by the Principal Investigator to the Clinical Research Unit of Guna S.p.a, through telephone, email, appropriate form and simultaneously through e-CRF.
- Serious Adverse Events (SAEs) and Suspected Serious and Unexpected Adverse Reactions (SUSARs) will have to be reported to the Sponsor immediately (within 24 h maximum) through telephone, email, appropriate form and simultaneously through e-CRF by the Principal Investigator and communicated to the Ethics Committee and the Ministry of Health.

Unità di Ricerca Clinica di GUNA S.p.a.

[contact]

mail: [contact]

[contact]

[contact]

Ufficio Farmacovigilanza di GUNA S.p.a.

[contact]

mail: [contact]

[contact]

The investigator should ensure that procedures are in place to ensure that the event is resolved.

In the case of nonserious Adverse Events (AEs), it is necessary to keep in mind that they can still give rise to serious events, which is why each Adverse Event must be monitored.

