Adverse Events that have not yet resolved at the end of the study will be followed up by the Investigator; each subject who has experienced an Adverse Event will be contacted at least once a month after the conclusion of the study for as many months as deemed appropriate.

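### Section 4.15 lets subjects leave the whole study after any adverse event without seeking their month-3 CMS, so the mean gain may be overstated if early leavers do worse

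*Combined protocol and SAP*

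**What the plan says.** Section 4.15 opens with "Subjects may leave the Clinical study for the following reasons" and lists three grounds: (a) the subject's own request, (b) the investigator's discretion, and (c) "if they experience an Adverse Event". Ground c has no limit on grade, seriousness or relation to the device. Section 6.4 defines an adverse event as "any harmful clinical event that will occur during the course of the clinical investigation", and its mild grade covers an event that "does not interfere with normal activities of daily living and resolves spontaneously". A minor, self-limiting event therefore meets ground c.

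The grounds concern the study, not the infiltrations. For a leaver, 4.15 asks for one item: "The reason for abandonment will be stated in the e-CRF".

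The infiltrations are given at day 0, week 2 and week 4 (4.9.1, 4.11). The CMS is measured at day 0 and months 3, 6 and 12 only (Table 1). The primary endpoint is the month-3 CMS against day 0 (4.13.2). Section 5.2.2 states: "The primary endpoint will be assessed by Student's t-test for paired data". Sections 5.1 to 5.2.3 give no analysis set, no rule for missing values, no sensitivity analysis and no allowance for dropout.

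**The concern.** A paired t-test needs a value at both times. A subject who leaves before month 3 has only the day-0 CMS, because no CMS is taken at weeks 2 or 4. With no rule for such subjects, the analysis falls back on those who stayed.

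If leaving is related to outcome, the completers' mean is not the mean of the 24 subjects treated. The trial has a single arm, so there is no comparison group in which similar losses might offset the error, and each subject is about 4% of the sample (1/24). Section 6.7 says that the final report aims at reliable conclusions on clinical efficacy, and the mean change is what carries them.

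The missing value would often be obtainable. The visit is already in the schedule, and a subject who has stopped infiltrations, or has already had all three, may be willing to attend it.

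**Working it through.** **1. The plan's own figure.** Inputs from 5.1: n = 24, difference 13, SD of differences 20. Alpha and sidedness are not stated; two-sided 0.05 is assumed. The non-centrality is 13/20 × √24 = 3.18 with 23 degrees of freedom. The non-central t gives a power of 86.19%, which matches the stated 86.2%. That figure uses all 24 enrolled, with no losses.

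**2. Mean over all subjects.** Let k of 24 leave before month 3 with true mean change c, and let completers gain 13, the effect assumed in 5.1. Then

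all-subject mean = ((24 − k) × 13 + k × c) / 24

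overstatement = (k/24) × (13 − c)

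The documents give neither k nor c, so the values below are assumptions chosen to show a range.

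| k | c | Calculation | All-subject mean | Overstatement |
|---|---|---|---|---|
| 3 | +13 | (273 + 39)/24 | 13.0 | 0 |
| 3 | +10 | (273 + 30)/24 | 12.6 | 0.4 |
| 3 | 0 | (273 + 0)/24 | 11.4 | 1.6 |
| 4 | −5 | (260 − 20)/24 | 10.0 | 3.0 |

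The complete-pairs analysis reports 13 in every row.

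**3. Effect on the test.** In 200,000 simulated trials of 24 normal changes with SD 20, leavers were drawn at random from the worse half of the changes. With a true mean of 0, the chance of a falsely significant gain rose from 2.5% with no leavers to 4.5% with 2 and 8.7% with 4. With a true mean of 13, the observed mean was 14.4 with 2 leavers and 16.1 with 4. As an upper bound, if exactly the worst changes are missing, the false-gain rate is 14.3% with 2 leavers and 34.9% with 4. If leaving is unrelated to outcome, there is no bias.

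**4. Power.** By the method of step 1, power is 80.9% with 21 pairs and 78.7% with 20. This follows from any loss of pairs, including withdrawal at the subject's own request. It is not specific to adverse events.

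**The case against.** Four points can be made for the plan.

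- **The wording is permissive.** A reader might infer that an adverse event removes the subject and the month-3 CMS. The text does not say so: subjects may leave, and one with a mild event can stay and be assessed. Nor does 4.15 forbid a later visit. This stands. What remains is that nothing asks for the visit once a subject has left.
- **Worse outcome in leavers is not shown.** A reader might infer that the t-test does overstate the gain. The documents do not support that. The adverse-event definition takes in events that have nothing to do with the shoulder, nothing links an event to a lower CMS, and exits after month 3 do not touch the primary endpoint. This also stands, so the bias is a plausible risk and not a result.
- **Safety follow-up exists.** A reader might infer that late safety information is lost in subjects who had events. Section 4.9.2 has all adverse events recorded from consent to the end of the investigation. Section 6.4 requires each event to be monitored and unresolved ones to be followed up, and says that "each subject who has experienced an Adverse Event will be contacted at least once a month after the conclusion of the study". At most, a new event in someone who has already left could be missed. These provisions do not mention the CMS, so they do not close the gap in the primary endpoint.
- **Ground a causes losses too.** Subjects may withdraw without giving a reason, and no wording can prevent that. This is why a missing-data rule is needed as well as better retention.

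**Conclusion.** The point holds as a conditional one. Section 4.15 makes any adverse event, and the investigator's discretion, a ground for leaving the whole study. No month-3 CMS is sought from leavers, and the primary test can use only complete pairs. The mean gain may therefore be overstated if those who leave before month 3 do worse than those who stay.

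The size cannot be derived from the documents. In the illustrations it runs from no bias to 3.0 points on a reported gain of 13. These rest on an assumed 3 or 4 leavers and an assumed change in leavers between −5 and +13. The fall in power is a separate consequence of any lost pairs. The change is worth making because it costs little, not because harm has been demonstrated.

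**What to change.** Add to 4.15 that subjects who stop treatment, or would leave early under ground b or c, are asked to attend the scheduled T3, T6 and T12 assessments unless they withdraw consent. State that this applies at any time, including after the third infiltration. By 4.9.2 the last infiltration is 2 months before the 3-month visit, so wording limited to subjects who stop infiltrations would miss exits during most of the period that matters. Add that any month-3 CMS so obtained enters the primary analysis.

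Add to 5.2.2 a simple sensitivity analysis for subjects whose month-3 CMS is still missing, for example with their change set to 0, which is the same as carrying the day-0 CMS forward. Zero is not a worst case if leavers deteriorate, so a negative value can be shown beside it.

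The rules on when infiltrations stop are left unchanged. The cost is wording in two sections, modest effort to bring subjects back to visits already scheduled, and possibly a slightly smaller reported gain.

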5 STATISTICS

5.1 Sample size

This is a one-sample study. We assume that at baseline the expected mean value of the Constant-Murley score is 65.0 and that given the eligibility criteria this value is between 50 and 80, we can therefore estimate the mean value to be 65.0 ± 7.5 .

It is also expected, that at the end of the treatment i.e. at months 3, using the alternative hypothesis $H_a: \Delta = 13$, compared to the null hypothesis $H_0: \Delta = 0$, estimating that the standard deviation of the differences is $s_{diff} \leq 20$. With these assumptions a sample of 24 patients has a power of 86.2% in discriminating a difference of 13 with a standard deviation of the differences of 20, if a Student's t-test for paired data is used. If the data were not Gaussian distributed, instead of using the nonparametric equivalent (Wilcoxon test, where the power would still be at least 82,8%), we would prefer - if possible - to use a non-linear transformation of the data.

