3.6.1 Selection Criteria

3.6.2 Inclusion Criteria

- Subjects with age > 18 years;
- Subjects with shoulder pain for at least 3 month;
- Subjects with a diagnosis of rotator cuff tendinopathy, subacromial conflict syndrome, partial rotator cuff tendon injuries (injuries A and B according to Snyder's Classification);
- Subjects with a CMS score between 40 and 75;
- Subjects who understood and signed the informed consent for active participation in the study;
- Subjects who are able to understand the conditions of the study and take part throughout the duration of the study.

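### Does the 50-80 baseline CMS range in section 5.1, which differs from the 40-75 entry criterion, undermine the 86.2% power claim?

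*Combined protocol and SAP*

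**What the plan says.** Section 5.1 opens with the design, "This is a one-sample study", and then describes the expected baseline. It states that "given the eligibility criteria this value is between 50 and 80, we can therefore estimate the mean value to be 65.0" and attaches a spread of 7.5 without labelling it as an SD.

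The entry criterion is given twice, in the synopsis and in section 3.6.2, in the same terms: "Subjects with a CMS score between 40 and 75".

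A separate sentence of 5.1 sets out the hypotheses (a mean change of 13 against 0) and introduces the variability of the change with "estimating that the standard deviation of the differences is" at most 20. The conclusion is "With these assumptions a sample of 24 patients has a power of 86.2% in discriminating a difference of 13", and that sentence goes on to name 20 as the SD of differences used. Section 5.2.2 assigns the paired t-test to the primary endpoint, "as already established in the section on sample size".

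**The concern.** There are two grounds for unease. First, 5.1 attributes to the eligibility criteria a range that they do not contain, and derives a baseline mean and spread from it. Power is then said to hold under the assumptions just listed, so a reader may suppose that the wrong range feeds the sample size.

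Second, the figure that is explained (65.0 ± 7.5) and the figure that drives power (an SD of differences of 20) seem unconnected, and the second has no citation, pilot data or assumed correlation. If 20 were too low, 24 patients would be too few. If it were generous, fewer would do. Because 5.2.2 refers back to 5.1, an unsound 5.1 might also seem to weaken the primary analysis.

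**Working it through.** **Inputs.** From 5.1: N = 24, mean change Δ = 13, SD of differences at most 20, paired t-test, stated power 86.2%, baseline range 50 to 80, baseline 65.0 ± 7.5. From the synopsis and 3.6.2: entry range 40 to 75. Assumed: two-sided alpha of 0.05, and ± 7.5 read as an SD.

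**1. Reproduce the stated power.** Power is the probability that a noncentral t variable with N − 1 degrees of freedom and noncentrality (Δ/SD)·√N falls outside the critical values.
- Noncentrality = (13/20)·√24 = 3.184, with 23 degrees of freedom.
- Two-sided 0.05 gives 0.8619, which matches 86.2%.
- One-sided 0.05 gives 92.6%, and the two-sided normal approximation gives 89.0%; neither matches. The unstated alpha can therefore be recovered from the figure itself.

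Neither 65.0 nor 7.5 appears in this formula.

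**2. Where 65.0 ± 7.5 comes from.**
- On 50-80: midpoint (50 + 80)/2 = 65.0; quarter-range (80 − 50)/4 = 7.5. Both match the text.
- On 40-75: midpoint (40 + 75)/2 = 57.5; quarter-range (75 − 40)/4 = 8.75.

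The mismatch is real. Replacing 65.0 ± 7.5 by 57.5 ± 8.75 leaves step 1 as it was, at N = 24 and 86.2%.

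**3. Could the wider entry range act indirectly, through the SD of differences?** Suppose 20 had been set with 50-80 in mind. Take the worst case, in which month-3 scores are unrelated to baseline, so that all the extra baseline variance passes into the difference. The new SD is then √(20² + new baseline variance − old baseline variance), with the same rule used for both ranges.
- Quarter-range rule: √(400 + 8.75² − 7.5²) = √(400 + 76.56 − 56.25) = 20.50; power 84.5%.
- Uniform scores: √(400 + 35²/12 − 30²/12) = √(400 + 102.08 − 75.00) = 20.67; power 83.9%.

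Even then the loss is about 2 percentage points.

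**4. Does 20 conflict with 7.5?** With s₀ and s₃ the SDs at baseline and month 3 and ρ their correlation, SD of differences = √(s₀² + s₃² − 2ρ·s₀·s₃). If both SDs were 7.5 (an assumption 5.1 does not make), the largest possible value is 15.0, at ρ = −1. That lies under the ceiling of 20, so the two statements are compatible, and power at 15 would be 98.2%.

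**5. How much room is there above 20?** At N = 24 and Δ = 13:

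| SD of differences | Power |
|---|---|
| 15 | 98.2% |
| 20 | 86.2% |
| 22 | 79.2% |
| 25 | 68.4% |

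Power reaches 80% at an SD of 21.77, and 21.77/20 = 1.09, so the ceiling could be exceeded by about 9% before power fell below 80%.

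**The case for a change.** The strongest opposing case is that the only variability input to a formal power claim is unsupported. An SD of differences of 25 instead of 20 would cut power to 68.4% and raise the N needed for 86.2% from 24 to 37. Section 6.7 says the final report is meant to support reliable conclusions on efficacy, so a pilot label does not fully excuse the omission. A corrected range, a source for the 20 and a line of sensitivity figures would cost little.

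Part of this stands. The range in 5.1 is wrong, the 20 has no source, and alpha is not stated. The rest does not carry. The 20 is presented as an upper limit, and nothing in the documents suggests that it will be exceeded. It need not follow from the 7.5, because 5.1 never says that it does; asking how large the month-3 SD must be to reach exactly 20 treats a ceiling as a point estimate. The power claim can be checked, and it reproduces to the stated precision. The power sentence names its own inputs, a difference of 13 and an SD of differences of 20, so the reference to preceding assumptions is loose wording and does not bring the baseline into the formula. Section 5.2.2 names the paired t-test itself, so the primary analysis does not depend on the baseline figures.

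**Conclusion.** This is a clerical inconsistency together with a planning assumption given without a source. The 50-80 range contradicts the 40-75 criterion, which is stated consistently in the synopsis and 3.6.2 and governs who is enrolled. The baseline figures drawn from the wrong range are descriptive only: correcting them changes the sample size by 0 and the stated power by 0 percentage points, and the entry criterion, the test and its interpretation stay as they are. Under the worst-case indirect route, power would be about 84%.

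The SD of differences is an unsourced upper limit with roughly 9% of headroom before power drops below 80%. Its basis would be useful background, but supplying it would not by itself alter anything the trial does, and the primary paired t-test will use the SD observed in the data. The conclusion rests on two-sided alpha of 0.05, inferred because it reproduces 86.2%, and, for the indirect check alone, on reading ± 7.5 as an SD. It would need revisiting only if evidence put the SD of differences above about 21.8; the documents contain none.

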5.2 Statistical analysis plan

5.2.1 Descriptive statistics

All data collected will be validated and subjected to descriptive case analysis. Categorical, nominal and ordinal variables will be summarised by relative and absolute frequency tables. Continuous variables will be described by mean (and 95% CI), median (and 95% CI), range, standard deviation and coefficient of variation.

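### Section 5.1 leaves the scale of the primary test to be chosen after the data are seen, and its Wilcoxon power figure is not the minimum it is said to be

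*Combined protocol and SAP*

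**What the plan says.** Section 5.1 plans a paired Student's t-test of zero mean change in CMS at month 3. It states that "a sample of 24 patients has a power of 86.2"% for "discriminating a difference of 13 with a standard deviation of the differences of 20". It then adds a conditional rule: "If the data were not Gaussian distributed, instead of using the nonparametric equivalent", given in brackets as the Wilcoxon test, "where the power would still be at least 82,8%), we would prefer - if possible - to use a non-linear transformation" of the data.

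Section 5.2.2 says only that the primary endpoint will be assessed by Student's "t-test for paired data as already established in the section on sample size". Nowhere does the plan name the transformation, the criterion for non-normality, the variable that is checked or transformed, what makes a transformation possible, or who decides and when.

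Section 5.2.1 keeps point-scale summaries ("Continuous variables will be described by mean (and 95% CI"), but only as descriptive statistics.

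**The concern.** There are two separate faults.

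**The primary test is not fixed.** Section 5.2.2 refers back to 5.1, and 5.1 contains the preference for a transformation. The analyst may therefore see the month-3 data, judge them non-Gaussian on a criterion of their own, and choose the scale. The stated null is zero mean change in CMS points, and the clinical thresholds are also in points (13 in the synopsis, 15 in section 4.13.2). A t-test on transformed scores tests that null only if the score distribution keeps its spread and shape between visits. If month 3 is more variable, a convex scale such as the square favours the device, and a concave one such as the log or square root works against it. The choice of scale thus sets the direction of the error.

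**The Wilcoxon power is presented as a minimum.** The sentence concerns non-Gaussian data, so its lower bound should hold for non-Gaussian shapes. It does not.

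**Working it through.** **Inputs.** From 5.1: n = 24, difference 13, SD of differences at most 20 with 20 used for power, and baseline "we can therefore estimate the mean value to be 65.0" ± 7.5. We read 7.5 as an SD because (80 − 50)/4 = 7.5. The significance level is not stated; we assume two-sided 5%.

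**The plan's power.** Noncentral t, n − 1 df, noncentrality (13/20)√n:
- n = 24: 86.19%. This reproduces the stated 86.2% and supports the two-sided 5% reading.
- n = 22.92 (24 × 3/π, the Wilcoxon large-sample efficiency for Gaussian data): 84.45%.
- n = 22: 82.81%. The plan's 82.8% is probably 22.9 rounded down to 22, although it shows no derivation.

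**Can the spread stay the same?** With ρ the correlation of change with baseline, month-3 variance = 7.5² + 20² + 2ρ × 7.5 × 20 = 456.25 + 300ρ.
- The month-3 SD is 12.5 at ρ = −1, 21.4 at ρ = 0 and 27.5 at ρ = +1.
- Equal spread needs ρ = −20/(2 × 7.5) = −1.33, which is impossible.
- For an SD of differences s, the condition is ρ = −s/15, so equal spread becomes possible only at s ≤ 15.
- Section 3.6.2 has a different range ("Subjects with a CMS score between 40 and 75"). Read the same way, the baseline SD is 35/4 = 8.75, the month-3 SD is 11.25 to 28.75, and equal spread needs ρ = −20/17.5 = −1.14, again impossible.

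**Size of the shift when mean change is zero.** On the squared scale the expected change equals the variance difference, 456.25 + 300ρ − 56.25 = 400 + 300ρ, so 100 to 700. Dividing by 2 × 65 = 130 gives 0.8 to 5.4 CMS points, and 3.1 at ρ = 0. To second order, the log scale shifts by the same amount the other way. The standard error of the mean change is 20/√24 = 4.1 points.

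**Illustrative error rates.** These assumptions are ours, not the plan's: mean change 0, change independent of baseline 65 ± 7.5, leave the raw t-test if Shapiro p < 0.05 on the differences, 30,000 trials per case. The table gives the chance of a false finding of benefit (nominal 2.5%).

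| Changes | Squared scores | Wilcoxon fallback | Raw t-test only |
|---|---|---|---|
| Left-skewed gamma, shape 2, SD 20 | 12.7% | 8.7% | 5.4% |
| Left-skewed gamma, shape 4, SD 20 | 8.5% | 6.0% | 4.4% |
| Left-skewed gamma, shape 2, SD 10 | 7.7% | 8.8% | 5.5% |
| Gaussian, SD 20 | 2.9% | 2.7% | 2.6% |

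In the left-skewed cases, log or square-root scales on the same gate give 3.5 to 4.8%, below the raw t-test.

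**Is 82.8% a minimum?** Exact signed-rank test at difference 13, SD 20, n = 24 (reject at T ≤ 81 or its mirror, actual level 4.91%), 200,000 trials per shape:

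| Shape of differences | Wilcoxon power |
|---|---|
| Gaussian | 84.6% |
| Beta(2,2) | 81.3% |
| Uniform | 79.4% |
| Beta(0.5,0.5) | 76.1% |
| Two clusters at ±0.9 SD | 74.3% |
| Two clusters at ±0.95 SD | 65.1% |
| t with 5 df | 90.2% |
| Laplace | 90.8% |

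T-test power in these symmetric shapes is 85.7 to 86.9%.

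**The case against.** Section 5.2.2 names one test, the paired t-test, and its reference to 5.1 may mean no more than the test used for power. That reading is possible, but the explicit preference in 5.1 still stands, and a t-test on transformed data is also a paired t-test. The text therefore does not exclude it.

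The 12.7% needs strong left skew, zero mean change, independence from baseline, a Shapiro gate, squaring, and the SD at its upper limit. That is fair: it is an illustration and not a forecast. At SD 10 squaring does less harm than the Wilcoxon fallback, and with Gaussian changes almost nothing happens. The spread argument likewise covers transformed scores only and weakens at an SD of differences of 15 or less. The missing specification does not depend on any of these cases.

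The raw t-test is not exact either. Under strong left skew it gives 5.4% against 2.5%, further from nominal than log or square-root scales, and its power is 81.3% against 87.3% for Wilcoxon. This stands. It makes the raw t-test a choice with a known cost, made for a null in CMS points fixed in advance. A transformation named in advance would also close the gap.

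The Wilcoxon figure changes no decision. Agreed.

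**Conclusion.** The concern holds on both parts. The first matters: the primary p-value could come from a scale, and so a null, picked with the data in view. At an SD of differences of 20 that choice can shift the result by 0.8 to 5.4 CMS points in either direction, against a standard error of 4.1. This rests on reading 7.5 as the baseline SD and on scores, not differences, being transformed. The illustrative error rates show what can happen under stated assumptions; they do not predict this trial. The descriptive means and intervals of 5.2.1 limit the damage to interpretation but do not protect the primary test.

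The second part is a false statement of modest consequence. Wilcoxon power falls about 1.5 to 3.4 points below 82.8% for beta(2,2) and uniform shapes, further for two-cluster shapes, and rises above it for heavy tails. The sample size of 24 and the 86.2% are unaffected. The point should be corrected, but it does not undermine the design.

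**What to change.** - **Section 5.2.2:** state that the primary analysis is the paired t-test on untransformed CMS change (month 3 minus baseline), reported as mean change with 95% CI in points, whatever the shape of the data.
- **Section 5.1:** delete the preference for a transformation. Drop the claim of a minimum and say that Wilcoxon power is about 84.5% if the changes are Gaussian and can be lower or higher for other shapes. Do not state a new floor.
- **Sensitivity analysis:** a Wilcoxon test or a bootstrap CI for the mean change may be added.
- **If a transformation is kept:** name in advance the transformation, what it is applied to, and the normality criterion.

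The cost is SAP wording only. The one downside is the raw t-test's behaviour under strong left skew: some excess false benefit and a few points less power than Wilcoxon, which itself has more false benefit there (8.7% on the same gate).
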